7 STUDY INTERVENTIONS DISCONTINUATION AND PARTICIPANT DISCONTINUATION/WITHDRAWAL

7.1 DISCONTINUATION OF STUDY INTERVENTIONS

The Sponsor, SDRT, PI, approving HREC(s), and the TGA independently reserve the right to discontinue the trial at any time for safety or other reasons. This will be done in consultation with the Sponsor where practical. In the event of premature trial termination or suspension, the above-mentioned parties will be notified in writing by the terminator/suspender stating the reasons for early termination or suspension (with the exception of the TGA as it is the Sponsor's responsibility to notify regulatory authorities). After a decision to prematurely terminate the trial or to suspend the trial, the Sponsor and the PI will ensure that adequate consideration is given to protecting the participants' interest and safety. The PI must review all participants as soon as practicable and complete all required records.

7.1.1 CRITERIA FOR ADMINISTRATION OF RESCUE MEDICATION INSTEAD OF IMP DOSING ON DAY 8

Once inoculated, it is expected that some study participants will experience malaria symptoms and biological changes (i.e. mild ALT/AST elevation, mild decrease in neutrophil count). Therefore, the following criteria should be considered as guidance for the decision not to proceed with pyronaridine dosing on Day 8 and preference for rescue medication instead:

1. A participant experiences an SAE or \geq CTCAE Grade 3 event (e.g. inoculum-related events such as lymphopenia or neutropenia).
2. A participant has an ALT or AST $> 2 \times$ ULN or total bilirubin $> 1 \times$ ULN.
3. A participant with positive alcohol or urine drug screen.
4. A participant who tests positive for SARS-CoV-2 (section 8.3.7).
5. A participant with one of the following ECG abnormalities:
 - QTcF at any time >480 msec,
 - Bundle branch block (except right bundle branch block that was present prior to pyronaridine administration),
 - Any arrhythmia, except:
 - a. *Sinus bradycardia that is clinically asymptomatic, and not associated with any other relevant ECG abnormalities,*
 - b. *sinus tachycardia that is clinically asymptomatic, and not associated with any other relevant ECG abnormalities,*
 - c. *Respiratory sinus arrhythmia,*
 - d. *Wandering atrial pacemaker,*

- e. *Isolated, single premature atrial/ventricular complex (i.e., no bigeminy, trigeminy, couplets, triplets or salvos) that does not occur more than once in a particular ECG tracing.*

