8.5.6 ADVERSE EVENT REPORTING

It is Investigator's responsibility to document and report all AEs occurring in the clinical trial whether spontaneously reported by the participant, observed by an Investigator (either directly or by laboratory or other assessments), or elicited by general questioning. The period of observation for collection of AEs extends from the time of inoculation with the malaria challenge agent to EOS. These AEs must be recorded on specific AE pages of the eCRF. Events reported prior to this will be recorded as medical history, unless the symptoms worsen during the trial.

The following information should be recorded for all AEs:

- Description
- Dates and times of onset and resolution
- Duration in hours
- Time of onset relative to IMP administration, inoculation with the malaria challenge agent, and/or administration of antimalarial rescue medications
- Seriousness (SAE or not)
- Severity
 - If severity of an AE changes, only one AE will be reported, with the highest severity recorded in the eCRF and listings and tables. In the clinical file (source data), the description of the AE will report the various severities observed over time.
 - If the AE resolves and then reoccurs, then two AEs will be reported.
- Action taken in response to the AE (including treatment given).
- Outcome.
- Relationship to the trial treatments or procedures (causality assessment), including malaria challenge agent, antimalarial medication, or any other treatment or procedure conducted during the trial.

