9.4.4 SAFETY ANALYSES

All descriptive statistics for safety parameters will be evaluated using the Safety Set.

All AE data will be listed for each volunteer, including severity, relationship to IMP (pyronaridine and malaria challenge agent), relationship to non-IMP protocol-specific treatments, outcome and actions taken. In addition, listings of AEs leading to discontinuation of the study, AESIs, SAEs and deaths, will be provided as applicable. Adverse events (AE) will be coded according to MedDRA and grouped by SOC and PT.

The main AE summaries will be restricted to Treatment Emergent Adverse Events (TEAEs) only, where a TEAE is defined as an AE that commences on, or after, the first administration of IMP up to the end-of-study (EOS) visit (inclusive). TEAEs without an onset date or time will be defined as treatment emergent except if an incomplete date (e.g., month and year) clearly indicates that the event started prior to first administration of IMP, or if the AE stop date indicates that the event stopped prior to the first administration of IMP.

At a minimum, the following AE summary tables will be provided:

- Overall summary of AEs
- All TEAEs
- TEAEs by severity
- TEAEs by relationship to the IMP
- TEAEs by relationship to rescue medications
- Serious TEAEs
- TEAEs leading to study withdrawal
- AESIs
- All Inoculation Period AEs
- Inoculation Period AEs by relationship to the malaria challenge agent

Lab parameters, physical examination, Body measurements, vital signs, Beck Depression inventory score and 12-lead ECG will be listed for all participants and visits. Summary tables for each scheduled visit, including observed values, change from each baseline and clinical significance of each abnormal value, will be presented.

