3.5.2 Secondary Endpoint (s)

3.5.2.1 Safety Parameters

The safety and tolerability of pyronaridine will be determined by recording the incidence, severity and relationship to pyronaridine of adverse events (as determined by clinical, laboratory and ECG examinations) from Day 8 up to Day 50±2.:

- AEs (including SAEs and AESIs)
- Vital signs
- 12-lead ECG
- Haematology, Biochemistry and Urinalysis
- Physical examination

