11.3.1 Adverse Events

AEs will be separated into two categories.

- Inoculum-emergent AEs (IEAEs)= AEs beginning any time from inoculation with the challenge agent until the end of study.
- Treatment-emergent AEs (TEAEs)= AEs beginning any time from administration of the IMP until the end of study.

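### Adverse events that start before dosing and worsen after pyronaridine are left out of every treatment-emergent table, because treatment emergence is defined by onset alone

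*SAP*

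**What the plan says.** Both documents define a treatment-emergent AE (TEAE) by when it starts. SAP 11.3.1 has "Treatment-emergent AEs (TEAEs)= AEs beginning any time from administration of the IMP until the end of study". Protocol 9.4.4 says that "a TEAE is defined as an AE that commences on, or after, the first administration of IMP". Neither adds a clause for events that worsen after dosing.

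The recording rule is in protocol 8.5.6: "If severity of an AE changes, only one AE will be reported, with the highest severity recorded in the eCRF and listings and tables". The only stated route to a second record is "If the AE resolves and then reoccurs, then two AEs will be reported". Collection starts well before pyronaridine: "The period of observation for collection of AEs extends from the time of inoculation with the malaria challenge agent to EOS". Dosing is on Day 8.

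SAP 11.3.1 has a second category, inoculum-emergent AEs (IEAEs), which runs from inoculation to the end of the study. Under SAP 11.3.1.2, the IMP-related summaries and the treatment-emergent (TE) SAE and AESI tables are all built on TEAEs. The IEAE set has its own severity, malaria-related, SAE and AESI tables, but no table of IMP-related IEAEs is planned.

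The endpoint that these tables serve is given in SAP 3.5.2.1 as "recording the incidence, severity and relationship to pyronaridine of adverse events", counted from Day 8 to Day 50±2.

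**The concern.** In most trials few events are under way at first dose. Here the participants are deliberately infected eight days earlier, and protocol 7.1.1 says: "Once inoculated, it is expected that some study participants will experience malaria symptoms and biological changes". It treats mild changes as compatible with dosing and diverts to rescue treatment only above stated limits. Participants can therefore receive pyronaridine with a low-grade event in progress.

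The two sources of events also overlap. Protocol 2.2.1 lists headache, vomiting, abdominal pain and neutropenia among the frequent events in its account of pyronaridine risk. Protocol 8.1.3 lists headache, vomiting and abdominal discomfort as malaria symptoms, and protocol 7.1.1 expects mild neutrophil falls after inoculation. If the drug makes such an event worse, the worsening falls inside the endpoint window but the onset rule keeps it out of the pyronaridine tables. At stake is whether those tables describe what happened after the drug was given, in a study with at most 18 participants.

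**Working it through.** The documents give no AE rate or other figure on this point, so there is nothing to reproduce. The check applies the two rules to concrete event patterns and then bounds the size.

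**Step 1. Inputs.**
- Record rule (protocol 8.5.6): one record at the highest grade if severity changes; two records if the event resolves and recurs.
- Onset rule (SAP 11.3.1, protocol 9.4.4): a TEAE if the recorded onset is on or after IMP administration.
- Maximum N = 18 (protocol 9.2); cohorts of up to 6 and proposed Cohort 1 groups of 2 (protocol 4.1).

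**Step 2. Apply the rules.** In each case the event starts at Grade 1 before dosing.

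| Course after dosing | Records | Highest IEAE grade | TEAE as written | TEAE with a worsening clause |
|---|---|---|---|---|
| Continuous, stays Grade 1 | 1 | 1 | none | none |
| Continuous, reaches Grade 2 | 1 | 2 | none | Grade 2 |
| Continuous, reaches Grade 3 | 1 | 3 | none | Grade 3 |
| Resolves, recurs after dosing at Grade 3 | 2 | 3 | Grade 3 | Grade 3 |

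Rows 2 and 3 are the gap. Row 1 shows that a worsening clause does not pull in stable events. Row 4 shows that recurrent events are already handled.

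**Step 3. Look for anything that puts rows 2 and 3 back.**
- Protocol 9.4.4 treats an AE without an onset date or time as a TEAE by default. That does not help when the pre-dose onset is known.
- Protocol 8.5.1 counts some worsening as an AE, but refers to pre-existing conditions or to the start of the trial, not to dosing; 8.5.6 then blocks a second record.
- SAP 11.3.1.1 listings show severity, relationship to IMP and onset relative to IMP, but not the grade at dosing or the date of the highest grade. A reader cannot see that the worst phase followed the drug.
- SAP 11.3.3 cross-tabulates laboratory abnormalities against the treatment baseline and summarises potentially clinically significant liver abnormalities (PCSA). These recover part of the laboratory signal.

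None of these returns the event to a pyronaridine AE table.

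**Step 4. Size per affected participant.** Change in incidence = 1/n:
- dose group of 2: 1/2 = 50 percentage points;
- cohort of 6: 1/6 = 16.7 points;
- all 18: 1/18 = 5.6 points.

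These are upper bounds. Overall incidence moves only if the participant has no other TEAE, and incidence of a term only if the participant does not already have that preferred term as a TEAE.

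**Step 5. Illustration under assumed rates.** Let q be the share of participants with at least one such event. The documents do not give q; 5% to 30% is assumed, with 18 participants dosed and independent of each other. Expected number = 18q; chance of at least one = 1 − (1 − q)^18.

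| Assumed q | Expected of 18 | Chance of at least one |
|---|---|---|
| 5% | 0.9 | 0.60 |
| 10% | 1.8 | 0.85 |
| 20% | 3.6 | 0.98 |
| 30% | 5.4 | 0.998 |

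**The case against.** The best defence is that the gap is narrow, and much of it stands.

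- **Laboratory events.** Protocol 8.5.1 says borderline laboratory findings should not routinely be recorded as AEs and gives CTCAE Grade 2 or above as its example of clinical significance. A mild ALT rise or neutrophil fall on Day 7 would usually not be an AE. If it first becomes reportable after dosing, the AE would normally start then and be a TEAE. The gap reaches only laboratory changes already judged reportable before dosing.
- **Frequency.** A reader might infer from protocol 7.1.1 that ongoing Grade 1 AEs at dosing are expected. It does not say that. It expects symptoms and mild changes in some participants, not that they are recorded as AEs or still present at dosing. Protocol 4.2 expects symptoms to be absent or mild on Day 8. The event must also rise in grade without first resolving, and headache or vomiting may come and go.
- **Nothing vanishes.** The event stays in the IEAE tables by dose group and maximum severity, and in the listings. It would also be wrong to say that its worst grade is credited to the challenge agent: IEAE is a timing category, and protocol 8.5.4.2 assesses relationship to each product separately.
- **Oversight.** Protocol 10.1.8 has the review team look at AEs, AESIs, SAEs and laboratory data between cohorts, so dose decisions do not depend on the TEAE tables. The endpoint is descriptive and secondary.

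These points limit the frequency and the consequences. They do not close the gap: a continuous AE with a known pre-dose onset that worsens after pyronaridine still appears in no treatment-emergent table.

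**Conclusion.** The concern holds as a gap in the definition, mainly for continuous symptoms. The direction is certain: the rule can only remove events from the pyronaridine tables. The amount is not. It is zero if no pre-dose event worsens, and no rate in the documents allows an estimate, so the Step 5 figures are illustrations only.

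Two stronger readings are tempting and unsupported. One is that pyronaridine AE incidence and severity are understated; the documents support only that they may be. The other is that a 50-point loss is typical. Groups of 2 are proposed only for Cohort 1, and SAP 4.2.4 tabulates by dose, so a dose repeated in a later cohort would give a larger group.

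The point should be fixed, but it does not threaten the primary PK/PD analysis.

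**What to change.** In SAP 11.3.1 and protocol 9.4.4, define a TEAE as an AE that starts on or after IMP administration, or that starts before it and afterwards increases in CTCAE grade, becomes serious or becomes an AESI.

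The single-record rule leaves the AE dataset without the data to apply this. Add the grade at IMP dosing and the date of maximum grade to the eCRF, or enter the post-dose worsening as a linked record with its own onset date. If an event may have peaked before dosing, eased and risen again, the highest grade after dosing is needed as well. Protocol 8.5.6 already keeps the severities over time in the source file, so no new assessment of participants is required.

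Cost: a sentence in each document, a small eCRF or completion-guideline change to a database that is already built, some back-entry from source, and approval of the protocol change under protocol 10.1.2. The linked-record option also changes the recording rule in 8.5.6; the added-fields option leaves it intact. TEAE counts may be slightly higher.

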11.3.1.1 AE Listings

All AE data will be listed for each participant and will include:

- IEAEs
- TEAEs
- IEAEs related to malaria
- TEAEs related to IMP
- IE SAEs (Serious adverse events)
- TE SAEs
- IEAEs leading to discontinuation or withdrawal
- TEAEs leading to discontinuation or withdrawal
- IE AESIs (Adverse Events of Special Interest)
- TE AESIs

Parameters to be included in the listings will be:

- Event Term
- Dates, times and study days of onset and resolution
- Severity (CTCAE Grades 1 to 5)
- Outcome (Not Recovered / Not Resolved; Recovered / Resolved; Recovered / Resolved with Sequelae; Recovering / Resolving; Fatal; Unknown)
- Relationship of AE to IMP (Not Related, Related)
- Relationship of AE to rescue medication (Not Related, Related)
- Relationship of AE to malaria challenge agent (Not Related, Related)
- Relationship of AE to study procedures (Not Related, Related)
- Action taken with IMP (No action taken; Rescue medication administered instead of IMP)
- Other actions taken (including withdrawal from the study)
- Seriousness (and Serious Adverse Event (SAE) criteria)

- AESI status (Yes/No)
- Relatedness to COVID-19 (Yes/No)

Derived parameters:

- Duration in hours
- Time in days of onset relative to first IMP administration

11.3.1.2 AE Tables

The number of events, as well as the number and percentage of participants experiencing an AE, will be summarised by, dose group and overall as follows:

Overall summary of IEAEs (FA set)

Overall summary of TEAEs (IMP set)

Summary of IEAEs by System Organ Class and Preferred Term (FA set)

Summary of TEAEs by System Organ Class and Preferred Term (IMP set)

Summary of IEAEs by System Organ Class, Preferred Term and Maximum Severity (FA set)

Summary of TEAEs by System Organ Class, Preferred Term and Maximum Severity (IMP set)

Summary of Malaria-Related IEAEs by System Organ Class and Preferred Term (FA set)

Summary of IMP-Related TEAEs by System Organ Class and Preferred Term (IMP set)

Summary of Malaria-Related IEAEs by System Organ Class, Preferred Term and Maximum Severity (FA set)

Summary of IMP-Related TEAEs by System Organ Class, Preferred Term and Maximum Severity (IMP set)

Summary of IE SAEs by System Organ Class and Preferred Term (FA set)

Summary of TE SAEs by System Organ Class and Preferred Term (IMP set)

Overall Summary of IE AESIs (FA set)

Overall Summary of TE AESIs (IMP set)

Summary of IE AESIs by System Organ Class and Preferred Term (FA set)

Summary of TE AESIs by System Organ Class and Preferred Term (IMP set)

For the summary tables, participants who experience the same AE (in terms of the MedDRA preferred term) more than once will only be counted once.

Additional summary tables of AEs related to rescue medications will be included if requested by MMV.

11.3.2 Concomitant Medication

Medications used in this study will be coded using WHO Drug Global version B3 Sep 2021 – Added Context.

Concomitant medications are defined as medications continued or newly received at or after administration of the malaria challenge agent through to the End of Study visit.

If a medication has a missing or partial missing start/end date or time and it cannot be determined whether it was taken before initial treatment or concomitantly, it will be considered as prior and concomitant.

Concomitant medications will be summarised by ATC and PN. The summary tables will show the number and percentage of participants taking each medication by ATC and PN.

For the summaries of concomitant medications, participants who take the same medication (in terms of the ATC and PN) more than once will only be counted once for that medication.

Use of rescue medications will be analysed as part of the treatment exposure analysis (Section 8).

11.3.3 Laboratory

Parameters

Hematology

- Basophils (absolute)
- Eosinophils (absolute)
- Haematocrit
- Haemoglobin
- Lymphocytes (absolute)
- Monocytes (absolute)
- Neutrophils (absolute)
- Platelet count
- Red blood cell count
- White blood cell count

Biochemistry

- Alanine Aminotransferase (ALT)
- Albumin
- Alkaline phosphatase (ALP)
- Aspartate Aminotransferase (AST)
- Bicarbonate
- Bilirubin (direct)
- Bilirubin (total)
- Calcium
- Calculated eGFR (CKD-EPI)
- C-Reactive protein
- Chloride
- Cholesterol Total
- Creatinine
- Creatine kinase
- Gamma Glutamyl Transpeptidase (GGT)
- Glucose (random and fasting)
- Glucose-6-phosphatase (G6PD)
- Lactate dehydrogenase (LDH)
- LDL
- HDL
- Phosphate
- Potassium
- Protein Total
- Sodium
- Triglyceride
- Troponin T/high sensitivity
- Urea
- Uric Acid

Pregnancy Test and FSH

β-Human Chorionic Gonadotropin (β-HCG) (women of child bearing potential only)
Follicular Stimulating Hormone (FSH) (post-menopausal women only)

Urinalysis

Dipstick Testing	Quantitative Assessments	Urine Chemistry
Red blood cells	Red blood cells	Glucose
Glucose	White blood cells	Protein
Ketone		
White blood cells		
Protein		
pH		
Red blood cells		
Glucose		
Ketone		

Coagulation

- International Normalized Ratio (INR)
- Activated Partial Thromboplastin Time (APTT)

Serology

- Hepatitis B surface antigen (HB sAG)
- Hepatitis C antibodies
- Red blood cell antibodies
- Anti-hepatitis B core antibodies (anti-HBc Ab)
- Human Immunodeficiency Virus (HIV) Ag/Ab 1/2 (anti-HIV1 and anti-HIV2 Ab)

Biostatistical methods

Listings

All laboratory parameters and change from treatment baseline values will be presented in data listings. Values outside the laboratory reference range will be listed with flags if considered low or high for values outside the reference ranges (where applicable) and if values considered to be clinically significant by the investigator.

Pregnancy test data will be listed only, for all women. FSH data will be listed only, for all post-menopausal women.

Coagulation data as well as qualitative and quantitative urinalysis data will also be listed only.

Tables

Haematology, biochemistry and continuous dipstick urinalysis laboratory data will be summarised for each scheduled visit, including observed values, absolute change from treatment baseline

Categorical dipstick urinalysis results will be summarised for each scheduled visit using frequency tabulations.

Laboratory abnormalities will be presented as cross-tabulations of the abnormality at each post-treatment baseline analysis visit versus the treatment baseline. Numbers of participants with treatment-emergent abnormalities will also be shown.

In addition, the liver function tests, namely AST, ALT, and total bilirubin, are used to assess possible drug-induced liver toxicity. The proportion of patients with Potential Clinically Significant Abnormality (PCSA) values at any post base line visit will summarized. The highest value of PCSA and time to the highest PCSA reading will also be summarized. Any of the following event will be considered as a PCSA:

- Any ALT or AST value above 5×ULN.
- An elevation in bilirubin 2×ULN.
- Any AST or ALT value above 2×ULN and (total bilirubin >1.5×ULN).
- Any AST or ALT value above 2×ULN with the appearance of fatigue, nausea, vomiting, right upper quadrant pain or tenderness, fever, rash and/or eosinophilia (eosinophil percent or count above the ULN).
- Constitutes a possible Hy's Law case
 - Hy's Law case is defined as a Participant with any value of alanine or aspartate aminotransferase greater than 3×ULN together with an increase in total bilirubin to a value greater than 2×ULN and not associated to an alkaline phosphatase value greater than 2×ULN (FDA Guidance on Drug Induced Liver Injury: Premarketing Clinical Evaluation [2009]).

11.4 Vital Signs

Parameters

- Systolic Blood Pressure (SBP) (mmHg)
- Diastolic Blood Pressure (DBP) (mmHg)
- Heart Rate (beats/minute)
- Temperature (°C)
- Respiratory rate (beats/min)

Biostatistical methods

All vital signs data will be listed for all participants. Any values outside of the protocol defined normal ranges will be flagged, with clinical significance status presented for out-of-range results.

Table 2: Vital Signs Normal Ranges

Parameter	Range
Systolic blood pressure	90-140 mmHg
Diastolic blood pressure	50-90 mmHg
Heart rate	50-100 bpm
Temperature	35.0-37.5°C
Respiratory rate	10-25 breaths/min

Vital sign parameters will be summarised by presenting summary statistics for observed values and change from treatment baseline values for each scheduled visit.

